### **Inclusion and Exclusion Criteria**

Inclusion: a) Being physically inactive (not performing 300 or 150 min of moderate or vigorous intensity physical activity respectively per week measured with the IPAQ questionnaire); b) BMI between 25 and 39.9 kg/m^2; c) Belonging to the cardiovascular health program of the External CESFAM of Valdivia d) Presenting with or without non-oncologic chronic pain.

Exclusion: a) Bone disease; b) Ischemic disease or arrhythmia and c) Chronic respiratory disease d) Uncontrolled chronic diseases f) People unable to understand instructions, g) People who do not speak Spanish h) History of previous oncological disease or under study for suspected neoplastic disease in any part of the body i) Low adherence to training (< 70% or non-attendance at 4 continuous sessions).

Included users will be divided into 3 groups: HIIT, ERE, and Control. All subjects will be evaluated at four times: pre-intervention (week 0 – time 1), week 4 (time 2), week 8 (time 3), and post-intervention (week 12 – time 4). Only the evaluation of metabolic flexibility and direct oxygen consumption will be carried out pre (week 0) and post-intervention (week 12).

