Regarding non-oncologic chronic pain, it is recognized as a disease in its own right (15), with a prevalence of 32.1% in the Chilean population (16), becoming a public health issue, negatively impacting quality of life, user function, representing a high socioeconomic burden (17, 18). Some metabolic disorders (e.g., diabetes mellitus, hypertension, and obesity) have been linked to the development and progression of non-oncologic chronic pain (9, 10, 11). Furthermore, individuals with non-oncologic chronic pain and cardiovascular diseases experience greater pain severity and disability than those with chronic pain alone (19). People with chronic pain often experience functional limitation, which is associated with low levels of physical activity, sedentary behavior, increasing the risk of developing cardiovascular diseases (19).

In this context, individuals with CRFs may enter the Cardiovascular Health Program (PSCV), which aims to reduce the incidence of cardiovascular events through the control and compensation of CRFs in primary care through the following actions:

- Reducing the cardiovascular risk of controlled individuals.
- Promoting healthy lifestyles.
- Achieving control of risk factors.
  - Achieving optimal blood pressure levels.
  - Improving metabolic control in people with diabetes.
  - Improving cholesterol levels in individuals with dyslipidemia.

Complementing the actions of the PSCV, physical exercise becomes a cornerstone for the control of these CRFs (20), improvement in metabolic flexibility (21), and reduction of non-oncologic chronic pain associated with CRFs (22, 23). Moderate-intensity aerobic exercise for 30 to 60 minutes every day of the week has been described as the most used alternative for controlling these risk factors (24); however, achieving this volume of exercise is very difficult in a clinical setting. Since lifestyle change is not easy for the population, adherence to some aerobic exercise programs decreases up to 50% in the first 3 months (25). Factors responsible for this low adherence include session duration, the presence of disease or post-exercise pain, and lack of time reported by users (26).

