## **Methodology**

The project formulation, planning, and management, the application of assessments, and exercise protocols will be carried out by a team of kinesiologists experienced in physical exercise and control of CRFs, supported by the Kinesiology school of the Universidad San Sebastián, Valdivia campus. This project will complement the actions of the PSCV of the External CESFAM of Valdivia. All evaluations and interventions will contribute to the Monthly Statistical Register (REM) of the PSCV, specifically, in the REM A27 (health education) section C (group physical activity for the cardiovascular health program) and, depending on the case, in REM A04 section B: Consultation with non-medical professionals. Both records will be collected by the providers (USS) and sent to the PSCV reference of the External CESFAM, ideally on the last day of the month, to contribute to REM. The results obtained during the intervention could be published in press articles, conferences, and renowned scientific journals to disseminate the good practices carried out by the CESFAM. The population will correspond to adult users of the PSCV enrolled in the External CESFAM of Valdivia with CRFs, the sample will be obtained through a public call inviting participation in HIIT or ERE exercise 3 sessions weekly for 12 weeks at the San Sebastián University Physical Fitness and Exercise Facility. The Cardiovascular Health Program team (Medical Director [name]) will identify eligible users

for the study within the records (clinical file and health controls) of the program, then the PSCV team will extend the invitation to users to participate in the project.

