### **Control Group:**

Participants in the control group will be requested to maintain their current lifestyle and exercise habits throughout the duration of the study. This includes adhering to their usual regimen of prescribed medication.

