## **Month 3**

- Pre-intervention evaluation (IPAQ, SF36, Cardiometabolic Variables, Metabolic Flexibility, and Pain)
- Exercise familiarization

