## **Months 4, 5, and 6**

- Application of training protocols
- Evaluation of workload adaptation every 4 weeks, until week 12 (Cardiometabolic Variables, Pain).

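### Low adherence to training is listed as an exclusion criterion, yet it can arise only after allocation and only in the two exercise arms, and nothing in the plan keeps low adherers in the randomised comparison

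*Combined protocol and SAP*

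**What the plan says.** The section Inclusion and Exclusion Criteria gives, as exclusion (i), "Low adherence to training (< 70% or non-attendance at 4 continuous sessions", alongside baseline conditions such as bone disease or not speaking Spanish. The next paragraph begins "Included users will be divided into 3 groups: HIIT, ERE, and Control" and continues "All subjects will be evaluated at four times" (weeks 0, 4, 8 and 12).

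The training against which adherence would be judged is described under Methodology as "HIIT or ERE exercise 3 sessions weekly for 12 weeks". Under Control Group the text is "Participants in the control group will be requested to maintain their current lifestyle and exercise habits throughout the duration of the study"; no sessions are offered to that arm.

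The Work Plan puts the baseline evaluation and "Exercise familiarization" in month 3. Training, with "Evaluation of workload adaptation every 4 weeks, until week 12", falls in months 4 to 6.

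The Statistical Analysis section randomises 64 people to each arm (58 plus a 10% dropout allowance). It relies on the random sequence and concealed envelopes to control selection bias, and it plans a group by time repeated-measures ANOVA. It does not mention intention to treat, any other analysis set, follow-up of people who meet criterion (i), or missing data.

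**The concern.** An eligibility criterion should be decidable before allocation. This one depends on behaviour after allocation, and only participants in HIIT and ERE can meet it. If it is applied as an exclusion, the exercise arms keep those who tolerated and attended the programme, while the control arm undergoes no such selection. Concealed allocation cannot prevent bias from removals made afterwards, so the protection that the Statistical Analysis section claims is lost for exercise versus control.

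HIIT versus ERE (Objective 1.2) is exposed too. Bias can arise if the two arms lose different numbers, or equal numbers for different reasons. The plan's own background section shows how varied the reasons may be: "Factors responsible for this low adherence include session duration, the presence of disease or post-exercise pain, and lack of time reported by users". Pain is also a study outcome, so at least one of these reasons is linked to what the trial measures.

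**Working it through.** **When and in whom the rule can be met**

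- Sessions: 3 per week x 12 weeks = 36 (Methodology).
- 70% of 36 = 25.2, so 25 attended (25/36 = 69.4%) meets the rule.
- Four consecutive absences also meet it: someone attending the other 32 (32/36 = 88.9%) would be excluded.
- Four sessions take 4/3 = 1.33 weeks, so the rule can be met before the week 4 visit.
- Control has 0 sessions, so the rule can never be met there.

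**Reproducing the plan's sample size**

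For the within-between interaction, λ = f²·N·m/(1 − ρ), df1 = (k − 1)(m − 1) and df2 = (N − k)(m − 1). The inputs k = 3, f = 0.10 and α = 0.05 come from Statistical Analysis, and m = 4 from the visit schedule. The plan does not give the correlation between visits or ε. Assuming ρ = 0.5 and ε = 1:

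- At N = 174, λ = 0.01 x 174 x 4/0.5 = 13.92 and power is 0.804, so the plan's 174 is reproduced.
- At N = 192, power is 0.848.

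The allowance for losses of every kind is 64 − 58 = 6 per arm, or 12 of 128 exercisers (9.4%). The plan gives no expected share of low adherers. Its remark that adherence can fall by up to 50% concerns other aerobic programmes.

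**Illustration of the bias**

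All of the following is assumed, not taken from the plan: 64 per arm, no true effect, ρ = 0.5, correlation r between adherence and change to week 12, and the lowest adherers removed from both exercise arms (58, 51 or 45 of 64 kept). With ρ = 0.5 the SD of change equals the outcome SD. The expected spurious change at week 12 is r x the mean standardised adherence of those kept. Type I error is by simulation of the sphericity-assumed group by time F test, 20,000 replicates per run. Ranges cover a linear build-up to week 12, a step from week 4, and repeat runs.

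| Exercisers removed | Spurious week-12 change, r = 0.3 | Type I error, r = 0.3 |
|---|---|---|
| 10% | 0.055 SD | 5.4-5.9% |
| 20% | 0.106 SD | 6.9-8.0% |
| 30% | 0.148 SD | 8.8-10.6% |

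- At 30% removed, r = 0.2 gives 6.4-7.5% and r = 0.4 gives 12.6-16.2%.
- If adherence relates only to a stable outcome level, not to change, type I error stays near 5%.
- The sign of the spurious change follows the sign assumed for r.

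**HIIT versus ERE, r = 0.3**

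- Equal removal for the same reasons: near 5%.
- 10% removed in one arm and 30% in the other: 6.5-7.1%.
- Equal removal of 10%, 20% or 30%, with adherence predicting change in one arm only: 5.6-5.7%, 7.3-7.8% or 8.3-9.5%.

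**Route out of the main test**

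A classical repeated-measures ANOVA uses only people with all values. For outcomes measured at four visits, anyone excluded and not evaluated afterwards drops out of the test, even if nobody deliberately deletes the data.

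**The case against.** The strongest reply is that the harm is inferred. No sentence says that low adherers' data are discarded or their visits stopped, and the statement that all subjects are evaluated four times points the other way. One could also read criterion (i) as applying to the month 3 familiarisation. It is fair that the documents show a misplaced criterion and an undefined analysis population, not an explicit adherers-only analysis. But the visit schedule does not say that an excluded person remains a subject. Familiarisation has no stated number of sessions and no link to (i), whereas the 70% and four-session thresholds fit a 36-session programme. The only written instruction is to exclude.

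Second, at the one loss rate the plan states (10%), the illustrated inflation is small, and larger figures need removal rates and correlations with no source in the plan. That stands: the case rests on the design defect, not on any particular percentage.

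Third, controls may also drop out, so the contrast is adherers versus controls still in follow-up. That is correct, but control losses are not selected by this rule. Likewise, the complete-case problem affects anyone who misses a visit and is a wider missing-data gap. Criterion (i) makes it one-sided. Outcomes measured only before and after training (SF36, metabolic flexibility, oxygen consumption) need only two visits, but exclusion before week 12 removes them as well.

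**Conclusion.** The concern holds. As written, criterion (i) is a post-allocation exclusion that can operate only in HIIT and ERE, and the plan contains nothing that returns those people to the as-randomised comparison. This follows from the text and needs no assumption beyond the rule being applied as the exclusion it is listed as. The size and direction of the bias are unknown. Under the stated assumptions it ranges from negligible (10% removed, or adherence unrelated to change) to roughly a doubling of the type I error (30% removed, r = 0.3), and more with a stronger correlation. The plan's figure of 174 is not in dispute here. The point should be settled before follow-up is lost, because visits not made cannot be recovered at analysis.

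**What to change.** 1. Remove (i) from the eligibility criteria. This need not change any rule for stopping training.
2. State that every randomised participant stays in the assigned group, is invited to the week 4, 8 and 12 evaluations whatever the attendance, and is included in the main analysis with all available visits. A mixed model with group, time and group by time would do this.
3. Use the 70% or four-consecutive-session threshold only to define a secondary per-protocol analysis, labelled as a non-randomised comparison.
4. Report how many people meet the threshold, with reasons, separately for HIIT and ERE.
5. Say whether f = 0.10 is meant for everyone randomised or for adherers. The plan cites only Cohen's classification, which does not settle this.

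**Cost.** Document wording, and the effort of inviting low adherers to visits already scheduled. The estimated effect may be smaller. If f = 0.10 describes everyone randomised, no extra participants are needed. If it was meant for adherers and falls to an assumed 0.09 or 0.08, power is 0.751 or 0.629 with all 192 analysed, and 0.700 or 0.578 with 174 analysed. Reaching 80% would then take 213 or 270 analysed, or 213/0.9 = 237 and 270/0.9 = 300 randomised at 10% dropout. These figures use ρ = 0.5 and ε = 1, as above.

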## **Statistical Analysis**

The sample size will be calculated as follows: (1) ANOVA for repeated measures with intra-inter-group interaction, (2) three groups, (3) type I error: 5%, (4) type II error: 20%, (5) statistical test power: 80%, and (6) effect size (ES): 0.10 according to Cohen's classification (1988). Using these parameters, the total sample size recommended by G\*Power software (Version 3.1.9.2) was 174 (58 per group). Assuming a 10% dropout, the total was calculated at 192, with 64 participants randomly assigned to each group. The concealment of allocation will be conducted by a researcher not involved in the clinical procedures of the intervention using the

method of opaque, sealed, and consecutively numbered envelopes. The random sequence and allocation concealment allow for the control of selection bias.

For enhanced bias control, the data analysis will be performed by a researcher blinded to the intervention groups. Dependent variables will be described in terms of mean and standard deviation. Assumptions of normality and homoscedasticity for all data will be verified using the Shapiro-Wilk test and the Levene's test, respectively. To address General Objective 1, the Student's t-test will be used to detect baseline differences between groups, and a repeated measures ANOVA (group x time) to determine differences in all dependent variables between training prior, and at 4, 8, and 12 weeks afterwards. The Bonferroni post hoc test will be used to test differences between groups. Additionally, the Cohen's d test will be applied to determine the effect size. To address the General Objective, the Pearson correlation test will be used to determine the relationship between MHR and the presence and intensity of non-oncological chronic pain. The level for statistical significance was set at  $p < 0.05$ . Statistical analyses will be performed using SPSS software version 21 (SPSS™ Inc., Chicago, IL, USA).

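### The low-adherence exclusion can act only after training starts and only in HIIT and ERE, and no analysis population is named that keeps those participants in the comparison with Control

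*Combined protocol and SAP*

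**What the plan says.** Under Inclusion and Exclusion Criteria, item (i) of the exclusions is "Low adherence to training (< 70% or non-attendance at 4 continuous sessions". The same section says "All subjects will be evaluated at four times", meaning weeks 0, 4, 8 and 12.

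The sessions in question are those of the exercise programme. Methodology describes a public call "inviting participation in HIIT or ERE exercise 3 sessions weekly for 12 weeks". Under Control Group, participants are "requested to maintain their current lifestyle and exercise habits throughout the duration of the study"; no sessions are offered to them.

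Statistical Analysis gives the sample size as 174 and continues: "Assuming a 10% dropout, the total was calculated at 192, with 64 participants randomly assigned to each group". It says of the allocation procedure: "The random sequence and allocation concealment allow for the control of selection bias". The analysis for General Objective 1 is "a repeated measures ANOVA (group x time) to determine differences in all dependent variables", with Bonferroni post hoc tests between groups. No analysis set is named, by assigned group or otherwise, and nothing is said about participants excluded under (i) or about missing visits.

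**The concern.** Attendance is not known at enrolment, so (i) is not an eligibility criterion in the usual sense. It removes people once the programme is running, and only the two exercise arms have sessions to miss. No exemption for illness or pain is stated.

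If those removed also leave the analysis, the exercise arms lose their poorest attenders while the corresponding people in Control stay in. If people who stop training would have done worse than those who continue, the results for pain, function and cardiometabolic risk are tilted towards exercise. If they would have done no differently, the means are not biased. The trial can tell these cases apart only if it still assesses those who stop. The planned ANOVA adds to the problem, because in its standard form it drops anyone with a missing visit.

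**Working it through.** **1. The plan's own sample size.** Inputs from Statistical Analysis: k = 3 groups, α = 0.05, power 80%, effect size 0.10 (read as Cohen's f). From Inclusion and Exclusion Criteria: m = 4 visits. The correlation between visits is not given; ρ = 0.5 with sphericity is assumed.

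- λ = f² × N × m/(1 − ρ); df1 = (k − 1)(m − 1) = 6; df2 = (N − k)(m − 1).
- N = 174: λ = 0.01 × 174 × 8 = 13.92, df2 = 513, power 0.804. N = 171 gives 0.796. So 174 is reproduced.
- 174 × 1.10 = 191.4, rounded up to 192 = 3 × 64. Reproduced.

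**2. How the rule acts.** Sessions: 3 × 12 = 36.

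- Run limb: four consecutive misses exclude someone who attends all the rest, (36 − 4)/36 = 88.9%. On a fixed schedule of three sessions a week, the fourth miss falls 7 days after the first.
- 70% limb, if counted over all 36 sessions: 10 misses leave 26/36 = 72.2% (stays); 11 misses leave 25/36 = 69.4% (excluded).
- Timing of the 70% limb alone: the quickest route to 11 misses without a run of four is three missed and one attended, three times over (9 misses in 12 sessions), then two more. That is session 14, in week 5, so these people have already passed the scheduled week-4 visit.

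Chance of meeting each limb, assuming independent misses (exact recursion for runs; binomial for 11 or more of 36):

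| Expected attendance | Four in a row | 11 or more misses |
|---|---|---|
| 90% | 0.3% | 0.06% |
| 80% | 4.2% | 8.9% |
| 70% | 17.7% | 53% |

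With scattered misses, a regular attender rarely meets either limb and would do so mainly through one block of absence. At 80% attendance or below, the 70% limb is the commoner trigger. These figures describe the rule and do not forecast attendance.

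**3. Bias, for illustration only.** Suppose there is no true effect, the least adherent share q of one exercise arm is dropped, and adherence correlates r with the outcome change. The shift is r × φ(z_q)/(1 − q) in SD units, where z_q is the normal quantile at q. With r assumed at 0.1 to 0.3:

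- q = 10%: 0.02 to 0.06 SD; two-sided type I error about 5% to 6%.
- q = 30%: 0.05 to 0.15 SD; about 6% to 12%.

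Neither q nor r is in the documents.

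**4. Power with and without those who stop.** There are 2 × 64 = 128 exercisers. Let p be the share who stop and b the share of benefit they keep. With everyone kept, the effect becomes f × (1 − p(1 − b)). No other missing data are assumed.

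| p | Dropped: N, power | Kept (192), b = 1 | Kept, b = 0.5 | Kept, b = 0 |
|---|---|---|---|---|
| 10% (13 of 128) | 179, 0.82 | 0.85 | 0.80 (f = 0.095) | 0.75 (f = 0.090) |
| 20% (26 of 128) | 166, 0.78 | 0.85 | 0.75 (f = 0.090) | 0.63 (f = 0.080) |

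**The case against.** The strongest reply is that the plan nowhere says excluded participants leave the assessments or the analysis, and "All subjects will be evaluated at four times" can be read as continued follow-up. This makes the harm conditional. It does not remove it: that sentence does not say that people excluded under (i) are still among the subjects, and a criterion headed as an exclusion is most naturally read the other way.

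A second reply is that the objectives concern adaptation to workload, so the effect in people who actually train is a fair target, and the only between-group comparison stated in the specific objectives is HIIT versus ERE, where the same rule applies to both arms. That stands as far as it goes. But the planned ANOVA includes Control, and for that contrast the rule is one-sided.

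Third, exercise familiarisation is scheduled before the training months and the moment of randomisation is not stated. Nothing, however, confines (i) to familiarisation.

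Four stronger readings are tempting but not supported:

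- A reader might infer that the rule removes people because of illness or post-exercise pain. The plan states no exemption, but it is equally silent on excused or make-up sessions.
- A reader might infer that the claim "The random sequence and allocation concealment allow for the control of selection bias" is false. It concerns allocation and remains true of allocation; it does not reach removals made later.
- A reader might take the background remark that "adherence to some aerobic exercise programs decreases up to 50% in the first 3 months" as a forecast of exclusions. It is an upper figure from other programmes, and the plan offers HIIT and ERE as time-effective alternatives.
- A reader might conclude that HIIT versus ERE is compromised. It is exposed only if exclusions differ between those arms.

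**Conclusion.** The concern holds. As written, the rule acts after training has begun and in two of three arms, and nothing in the plan keeps those affected in the analysis. If they are dropped, the exercise-versus-Control comparison is no longer between the groups formed by randomisation. This is a stated rule that can bias a result, so it should be changed and not merely clarified.

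A reader might go further and call the trial's results biased. The documents do not support that: they give neither the number who will meet the thresholds nor how their outcomes would differ. The illustrative shifts are small at 10% excluded and grow with the share removed. The conclusion rests on the natural reading of an exclusion criterion. The power figures rest on ρ = 0.5, f = 0.10, sphericity and illustrative stopping rates.

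**What to change.** 1. Move (i) out of the exclusion criteria. Restate it as a rule for stopping training and as the definition of a secondary per-protocol set, reported as not being a randomised comparison with Control. Simple deletion would leave no rule for prolonged absence.
2. State that everyone randomised stays in the week 4, 8 and 12 assessments as far as is safe, whether or not training has stopped.
3. Make the primary Objective 1 analysis by assigned group, with a mixed model for repeated measures (group, time, group × time), so that participants with incomplete visits are not dropped. This is valid if missingness is explained by observed data, which is another reason to keep assessing those who stop.
4. Report by arm how many met each threshold, and the reasons for absence.

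The cost is a short amendment, some follow-up of people who stopped training (at visits already planned) and a different model. The real downside is dilution: in the least favourable case tabulated, with 20% stopping and gaining nothing, power is 0.63. That loss reflects a truly smaller average effect in everyone assigned to exercise. Visits not made cannot be recovered, so the rule should be settled before anyone is removed under it.
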